7.2.11 Columbia Suicide Severity Rating Scale (C-SSRS)

The C-SSRS is a clinical rating of suicidal behavior and ideation. The C-SSRS consists of a maximum of 20 items. The Baseline/Screening version of the C-SSRS will be administered at screening (Day -21 to -2), while the Since Last Visit version of the C-SSRS will be administered at the other time points on the Schedule of Assessments (Table 2 and Table 3). Reports of suicidal ideation with intent to act (endorse item 4 or 5) and reports of actual, aborted, or interrupted suicide attempts or a behavior preparatory for making an attempt indicate subjects at high risk for suicide. If such reports are identified, the investigator is to appropriately manage the subject in accordance with standard of care.

An example of the C-SSRS is presented in Appendix E and Appendix F.

7.2.12 Headache Questionnaire

Subjects will be asked questions from the headache questionnaire as indicated in the Schedule of Assessments (Table 2 and Table 3) and site to record information, such as the date of headache, severity of pain, headache symptoms, and medications taken on the headache questionnaire and in the applicable Adverse Event or Concomitant Medication eCRF page. An example of the headache questionnaire can be found in

Appendix D. The headache questionnaire can be updated during the study at the discretion of the MM.

7.2.13 Height, Weight, and Body Mass Index

Height in centimeters will be measured without shoes at screening.

Weight in kilograms will be measured without shoes at time points specified in the Schedule of Assessments (Table 2 and Table 3).

Subject BMI will be calculated using height and weight measurements taken at screening according to the following formula:

BMI (kg/m^2) = weight $(kg)/(height [cm]/100)^2$

7.2.14 Neurological Examination

A neurological examination including assessment of cranial nerves, motor system, sensory system (including testing for pain sensation [pin prick], light touch sensation [brush], von Frey, and vibratory sense), reflexes, and cerebellar function will be performed by the principal investigator or qualified physician as indicated in the Schedule of Assessments (Table 2 and Table 3).

The individual performing the neurological examination will characterize their findings as either normal or abnormal. Any subjects with abnormal findings found during baseline will not be allowed to enroll in the study. Abnormal findings found after subject has received study medication will be reported on the adverse event eCRF.

7.2.15 Electrocardiograms

During the study, 12-lead electrocardiograms (henceforth referred to as electrocardiogram or ECG) will be performed at the time points indicated in the Schedules of Assessments (Table 2 and Table 3).

The subject must be in supine position in a rested and calm state for at least 5 minutes before ECG assessment is conducted. If the subject is unable to be in the supine position, the subject should be in most recumbent position as possible.

At Screening, ECGs will be performed in a standardized method, in triplicate, and approximately 30 seconds apart, prior to blood draws or other invasive procedures. From Day 1 to EOS visit, ECGs will be performed as a single electrocardiogram. Each ECG must include the following measurements: QRS, QT, QTc, RR, and PR intervals.

The Principal Investigator or designated site physician will review all ECGs. Once signed, the original ECG tracing will be retained with the subject's source documents. At the request of the sponsor, a copy of the original ECG will be made available to Amgen.

7.2.16 Creatinine Clearance

For determining eligibility, estimated glomerular filtration rate (eGFR) will be calculated by the estimated **Modification of Diet in Renal Disease (MDRD) formula** based on serum creatinine, age, sex and race values at time points indicated in the Schedule of Assessments (Table 2 and Table 3).

7.2.17 Clinical Chemistry

Blood samples for clinical chemistry will be collected at time points specified in the Schedule of Assessments (Table 2 and Table 3). All laboratory tests must be reviewed and signed by the principal investigator or qualified designee. Additional safety laboratory assessments may be performed for subject safety.

The tests listed below will be conducted and analyzed by standard laboratory procedures:

Albumin	Blood urea nitrogen (BUN) or Urea
Calcium	Chloride
Glucose	Phosphorus or Phosphate
Potassium	Creatinine
Magnesium	Sodium
Carbon Dioxide or Bicarbonate	Uric acid
Aspartate aminotransferase (AST / SGOT)	Alanine aminotransferase (ALT / SGPT)
Cholesterol	Total bilirubin (TBIL)
Alkaline phosphatase (ALP)	Direct bilirubin
Total protein	Triglycerides
High-density lipoprotein (HDL)	Creatinine Phosphokinase (CPK)
Cardiac enzymes (CPK-MB and Troponin I or Troponin T)	Hemoglobin A1C

Table 4. Clinical Chemistry

7.2.18 Hematology

Blood samples for hematology tests will be collected at time points specified in the Schedule of Assessments (Table 2 and Table 3). All laboratory tests must be reviewed and signed by the principal investigator or qualified designee. Additional safety laboratory assessments may be performed for subject safety.

The tests listed below will be conducted and analyzed by standard laboratory procedures:

Red blood cells	White Blood Cell (WBC)
Hemoglobin	White blood cells differential count:
Hematocrit	 Total neutrophils (OR segmented neutrophils and band cells)
Mean corpuscular volume	Eosinophils
Mean corpuscular hemoglobin	Lymphocytes
Platelet count	Basophils
Mean corpuscular hemoglobin concentration	Monocytes

Table 5. Hematology

7.2.19 Urinalysis

Urine samples will be collected at time points specified in the Schedule of Assessments (Table 2 and Table 3).

All laboratory tests must be reviewed and signed by the principal investigator or qualified designee. Additional safety laboratory assessments may be performed for subject safety.

The tests listed below will be conducted and analyzed by standard laboratory procedures:

Specific gravity	рН						
Blood	Protein						
Glucose	Ketones						
Bilirubin	Urobilinogen						
Microscopic exam (performed at the discretion of the principal investigator or qualified designee):							
White blood cells	Red blood cells						
Epithelial Cells	Bacteria						
Casts	Crystals						

Table 6. Urinalysis

7.2.20 Drug, Alcohol, and Cotinine Screen

Drug, alcohol, and cotinine assessments are to be completed at time points indicated in the Schedule of Assessments (Table 2 and Table 3). The drug and alcohol tests will include testing for drugs with a high potential for abuse, including amphetamines, barbiturates benzodiazepines, cocaine, ethanol, opiates, and tetrahydrocannabinol.

Subjects who test positive for drug, alcohol, and cotinine will not qualify for study product administration. Subjects with a positive drug test may be retested once at the discretion of the investigator.

7.2.21 Hepatitis B Surface Antigen, Hepatitis C Antibody and HIV Status

Hepatitis B surface antigen and core antibody, HepCAb, and HIV status will be assessed at time points indicated in the Schedule of Assessments (Table 2 and Table 3) and must be confirmed negative to be eligible for this study.

7.2.22 Menopausal Status Test

Additional tests to confirm postmenopausal status will be performed for any women age < 55 years and with spontaneous menses within the past 1 year, but currently amenorrheic (eg, spontaneous or secondary to hysterectomy). Postmenopausal gonadotropin levels (luteinizing hormone and follicle-stimulating hormone levels > 40 IU/L) or postmenopausal estradiol levels (< 5 ng/dL), or according to the definition of "postmenopausal range" for the laboratory involved, must be consistent with postmenopausal status per local laboratory ranges to be eligible for this study. Postmenopausal status will be recorded on the medical history eCRF.

7.2.23 Pregnancy Test

A serum or highly sensitive urine pregnancy test will be collected at Day -1 and EOS as specified in the Schedule of Assessments (Table 2 and Table 3). The screening (serum) and Day -1 (serum or urine) pregnancy test must be confirmed negative to be eligible for this study.

7.2.24 Blood Sample Collection for AMG 334 Serum Concentrations

Blood samples will be collected for determination of AMG 334 serum concentrations at time points indicated in the Schedule of Assessments (Table 2). Sample collection, handling, and shipping procedures are specified in a separate manual.

7.2.25 Blood Sample Collection for CGRP Concentrations

Blood (plasma) samples will be collected for determination of CGRP concentrations at the time points indicated in the Schedule of Assessments (Table 2 and Table 3). Detailed instructions outlining the collection, processing and shipping of the CGRP samples are located in a separate manual.

7.2.26 Blood Sample Collection for PACAP-38 Concentrations

Blood samples for PACAP-38 plasma concentrations will be collected for all subjects at time points specified in the Schedule of Assessments (Table 2 and Table 3). Detailed

instructions on sample collection, processing, and shipping will be provided in a separate manual.

7.3 Antibody Testing Procedures

Blood samples for antibody testing will be collected at time points specified in the Schedule of Assessments (Table 2) for the measurement of anti-AMG 334 binding antibodies. Samples testing positive for binding antibodies will also be tested for neutralizing antibodies and may be further characterized for quantity/titer, isotype, affinity, and presence of immune complexes. Additional blood samples may be obtained to rule out anti-AMG 334 antibodies during the study.

Sites will be notified of any positive neutralizing antibody results to AMG 334. If results are not provided, no neutralizing antibodies to AMG 334 have been detected.

Subjects who test positive for neutralizing antibodies to AMG 334 at the final scheduled study visit will be asked to return for additional follow-up testing. This testing is to occur approximately every 3 months starting from when the site has been notified of the positive result, until: (1) neutralizing antibodies are no longer detectable or (2) the subject has been followed for a period of at least 1 year (± 4 weeks) post administration of AMG 334. All follow-up results, both positive and negative will be communicated to the sites. More frequent testing (eg, every month) or testing for a longer period of time may be requested in the event of safety-related concerns. Follow-up testing is not required where it is established that the subject did not receive AMG 334.

Subjects who test positive for binding, non-neutralizing antibodies and have clinical sequelae that are considered potentially related to an anti-AMG 334 antibody response may also be asked to return for additional follow-up testing. Refer to the Schedule of Assessments (Table 2), as applicable, for specific time points and the laboratory manual for detailed collection and handling instructions.

7.4 Biomarker Development

Biomarkers are objectively measured and evaluated indicators of normal biologic processes, pathogenic processes, or pharmacologic responses to a therapeutic intervention. Biomarker development can be useful in developing markers to identify disease subtypes, guide therapy, and/or predict disease severity.

Amgen may attempt to develop test(s) designed to identify subjects most likely to respond positively or negatively to AMG 334.

Blood Samples

Blood samples are to be collected for biomarker development at the time points in the Schedule of Assessments (Table 2 and Table 3).

7.5 Pharmacogenetic Studies (Optional)

If the subject consents to the optional pharmacogenetic portion of this study, DNA analyses may be performed. These optional pharmacogenetic analyses focus on inherited genetic variations to evaluate their possible correlation to the disease and/or responsiveness to the therapies used in this study. The goals of the optional studies include the use of genetic markers to help in the investigation of study indications (eg, migraines), neurological diseases, and/or AMG 334 immunogenicity, and/or in the identification of subjects who may have positive or negative response to AMG 334. For subjects who consent to this/these analysis/analyses, DNA may be extracted. Refer to the central laboratory manual for details regarding the collection, processing and shipping of the pharmacogenetic samples.

7.6 Sample Storage and Destruction

Any blood sample collected according to the Schedule of Assessments (Table 2 and Table 3) can be analyzed for any of the tests outlined in the protocol and for any tests necessary to minimize risks to study subjects. This includes testing to ensure analytical methods produce reliable and valid data throughout the course of the study. This can also include, but is not limited to, investigation of unexpected results, incurred sample reanalysis, and analyses for method transfer and comparability.

All samples and associated results will be coded prior to being shipped from the site for analysis or storage. Samples will be tracked using a unique identifier that is assigned to the samples for the study. Results are stored in a secure database to ensure confidentiality.

If informed consent is provided by the subject, Amgen can do additional testing on remaining samples (ie, residual and back-up) to investigate and better understand migraine pain, the dose response and/or prediction of response to AMG 334, characterize antibody response, and characterize aspects of the molecule (eg, mechanism of action/target, metabolites). Results from this analysis are to be documented and maintained, but are not necessarily reported as part of this study. Samples can be retained for up to 20 years.

Since the evaluations are not expected to benefit the subject directly or to alter the treatment course, the results of pharmacogenetic, biomarker development, or other exploratory studies are not placed in the subject's medical record and are not to be made available to the subject, members of the family, the personal physician, or other third parties, except as specified in the informed consent.

The subject retains the right to request that the sample material be destroyed by contacting the investigator. Following the request from the subject, the investigator is to provide the sponsor with the required study and subject number so that any remaining blood samples and any other components from the cells can be located and destroyed. Samples will be destroyed once all protocol-defined procedures are completed. However, information collected from samples prior to the request for destruction, will be retained by Amgen.

The sponsor is the exclusive owner of any data, discoveries, or derivative materials from the sample materials and is responsible for the destruction of the sample(s) at the request of the subject through the investigator, at the end of the storage period, or as appropriate (eg, the scientific rationale for experimentation with a certain sample type no longer justifies keeping the sample). If a commercial product is developed from this research project, the sponsor owns the commercial product. The subject has no commercial rights to such product and has no commercial rights to the data, information, discoveries, or derivative materials gained or produced from the sample. See Section 11.3 for subject confidentiality.

8. WITHDRAWAL FROM TREATMENT, PROCEDURES, AND STUDY 8.1 Subjects' Decision to Withdraw

Subjects have the right to withdraw from the study at any time and for any reason without prejudice to their future medical care by the physician or at the institution.

Withdrawal of consent for a study means that the subject does not wish to receive further protocol-required therapies or procedures, and the subject does not wish to or is unable to continue further study participation. Subject data up to withdrawal of consent will be included in the analysis of the study, and where permitted, publically available data can be included after withdrawal of consent. The investigator is to discuss with the subject appropriate procedures for withdrawal from the study.

8.2 Investigator or Sponsor Decision to Withdraw or Terminate Subjects' Participation Prior to Study Completion

The investigator and/or sponsor can decide to withdraw a subject(s) from investigational product and/or other protocol required therapies, protocol procedures, or the study as a whole at any time prior to study completion.

Subjects may be eligible for continued treatment with Amgen investigational product(s) and/or other protocol required therapies by a separate protocol or as provided for by the local country's regulatory mechanism, based on parameters consistent with Section 12.1.

8.3 Reasons for Removal From Treatment or Study

8.3.1 Reasons for Removal From Treatment

Reasons for removal from protocol-required investigational product(s) or procedural assessments include any of the following:

- subject request
- safety concern (eg, due to an adverse event, ineligibility determined, protocol deviation, non-compliance, requirement for alternative therapy, protocol-specified criteria, pregnancy)
- death
- lost to follow-up
- decision by sponsor (other than subject request, safety concern, lost to follow-up)

8.3.2 Reasons for Removal From Study

Reasons for removal of a subject from the study are:

- decision by sponsor
- withdrawal of consent from study
- death
- lost to follow-up

9. SAFETY DATA COLLECTION, RECORDING, AND REPORTING

9.1 Definition of Safety Events

9.1.1 Disease-Related Events

Disease-Related Events are events (serious or non-serious) anticipated to occur in the study population due to the underlying disease. Such events do not meet the definition of an Adverse Event unless assessed to be more severe than expected by the investigator for the subject's condition.

Disease-Related Events and/or Disease-Related Outcomes that do not qualify as Serious Adverse Events:

- An event which is part of the normal course of disease under study (eg, disease progression in oncology or hospitalization due to disease progression) is to be reported as a Disease-Related Event.
- Death due to the disease under study is to be recorded on the Event CRF.

If the outcome of the underlying disease is worse than that which would normally be expected for the subject, or if the investigator believes there is a causal relationship between the investigational product(s)/study treatment protocol required therapies and disease worsening, this must be reported as an Adverse Event or Serious Adverse Event.

9.1.2 Adverse Events

An adverse event is defined as any untoward medical occurrence in a clinical trial subject. The event does not necessarily have a causal relationship with study treatment. The investigator is responsible for ensuring that any adverse events observed by the investigator or reported by the subject are recorded in the subject's medical record.

The definition of adverse events includes worsening of a pre-existing medical condition. Worsening indicates that the pre-existing medical condition or underlying disease (eg, diabetes, migraine headaches, gout) has increased in severity, frequency, and/or duration more than expected by the investigator's assessment. A pre-existing condition that has not worsened more than anticipated (ie, more than usual fluctuation of disease) during the study, or involves an intervention such as elective cosmetic surgery or a medical procedure while on study, is not considered an adverse event.

The investigator's clinical judgment is used to determine whether a subject is to be removed from treatment due to an adverse event. In the event a subject, or subject's legally acceptable representative requests to withdraw from protocol-required therapies or the study due to an adverse event, refer to Section 8.1 for additional instructions on the procedures recommended for safe withdrawal from protocol-required therapies or the study.

Migraines and non-migraine headaches are study endpoints.

9.1.3 Serious Adverse Events

A serious adverse event is defined as an adverse event that meets at least 1 of the following serious criteria (unless it meets the definition of a Disease-Related Event as defined in Section 9.1.1):

- fatal
- life threatening (places the subject at immediate risk of death)
- requires in patient hospitalization or prolongation of existing hospitalization
- results in persistent or significant disability/incapacity
- congenital anomaly/birth defect
- other medically important serious event

A Disease-Related event is to be reported as a serious adverse event if,

- the subject's pre-existing condition becomes worse than what the investigator would consider typical for a patient with the same underlying condition, or
- if the investigator believes a causal relationship exists between the investigational medicinal product(s)/protocol-required therapies and the event,
- and the event meets at least 1 of the serious criteria above.

An adverse event would meet the criterion of "requires hospitalization", if the event necessitated an admission to a health care facility (eg, overnight stay).

If an investigator considers an event to be clinically important, but it does not meet any of the serious criteria, the event could be classified as a serious adverse event under the criterion of "other medically important serious event". Examples of such events could include allergic bronchospasm, convulsions, blood dyscrasias, drug induced liver injury (DILI) (see Appendix A for DILI reporting criteria), or events that necessitate an emergency room visit, outpatient surgery, or urgent intervention.

9.2 Safety Event Reporting Procedures

9.2.1 Disease-Related Events

Migraine is considered a disease related event; however, worsening of migraine (ie, increased in severity, frequency, and/or duration more than expected by the investigator's assessment) should be reported as an AE.

9.2.2 Adverse Events

9.2.2.1 Reporting Procedures for Adverse Events That do not Meet Serious Criteria

The investigator is responsible for ensuring that all adverse events observed by the investigator or reported by the subject that occur after first dose of investigational product through the EOS are reported using the Adverse Event CRF.

The investigator must assign the following adverse event attributes:

- Adverse event diagnosis or syndrome(s), if known (if not known, signs or symptoms)
- Dates of onset and resolution (if resolved)
- Severity
- Assessment of relatedness to investigational product
- Action taken

The adverse event grading scale used will be the Common Terminology Criteria for Adverse Events (CTCAE). The grading scale used in this study is described in Appendix A. The investigator must assess whether the adverse event is possibly related to the investigational product, and/or other protocol-required therapies. This relationship is indicated by a "yes" or "no" response to the question: Is there a reasonable possibility that the event may have been caused by the investigational product, and/or other protocol-required therapies?

The investigator must assess whether the adverse event is possibly related to any study mandated activity (eg, administration of investigational product, protocol-required therapies, device(s) and/or procedure (including any screening procedure(s)). This relationship is indicated by a "yes" or "no" response to the question: "Is there a reasonable possibility that the event may have been caused by a study activity (eg, administration of investigational product, protocol-required therapies, device(s)), and/or procedure"?

The investigator is responsible for reviewing laboratory test results and determining whether an abnormal value in an individual study subject represents a clinically significant change from the subject's baseline values. In general, abnormal laboratory findings without clinical significance (based on the Investigator's judgment) are not to be recorded as adverse events. However, laboratory value changes that require treatment or adjustment in current therapy are considered adverse events. Where applicable,

clinical sequelae (not the laboratory abnormality) are to be recorded as the adverse event.

The investigator is expected to follow reported adverse events until stabilization or reversibility.

MLA and non-migraine headaches should be recorded on the headache questionnaires and on the adverse event eCRF page.

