4.2 Planned Covariates and Subgroups

Planned covariates consist of baseline measures. No subgroup analysis is planned.

5. Hypotheses and/or Estimations

A single dose of 140 mg IV of AMG 334 will inhibit MLAs in subjects challenged with PACAP-38.

6. Definitions

Adverse Event (AE)

Serious Adverse Event (SAE):

SAE determined by the flag indicating if the adverse events is serious on the AE eCRF page will include these that occur after signing the informed consent and up to and including end of study (EOS).

Treatment-Emergent AE:

A treatment-emergent AE is that occurs on or after the initial dose of investigational product (IP) as determined by the flag indicating if the AE started prior to the first dose on the AE eCRF and up to and including end of study.

Disease-Related AE:

Migraine will be considered a disease related event; however, worsening of migraines (ie. increased frequency and/or intensity) should be reported as an AE.

Baseline

Unless otherwise stated, baseline will be defined as the last assessment taken prior to the first IP (AMG 334 or placebo) administration (ie, Day 1 pre-dose or Screening if Day 1 pre-dose is not available).

Statistical Analysis Plan: 20140207

Date: 17 May 2017 Page 15

Change from Baseline:

The arithmetic difference between a post-baseline value and the baseline value:

Change (absolute) from Baseline = (Post-baseline Value – Baseline Value)

Change (percent) from Baseline = [(Post-baseline Value – Baseline Value) / Baseline Value] x 100

Body Mass Index (BMI)

BMI will be calculated as {weight (kg)/ [height (m)]²} in the clinical database.

Columbia Suicide Severity Rating Scale (C-SSRS)

The C-SSRS is a clinical rating of suicidal ideation and behavior. Refer to Appendix E and Appendix F in the protocol for complete details on the C-SSRS. The Baseline/Screening version of the C-SSRS will be administered at screening (Day -21 to -2), while the Since Last Visit version of the C-SSRS will be administered at the other time point(s) on the Schedule of Assessments. Reports of suicidal ideation with intent to act (endorse item 4 or 5) and reports of actual, aborted, or interrupted suicide attempts or a behavior preparatory for making an attempt indicate subjects at high risk for suicide. If such reports are identified, the investigator is to appropriately manage the subject in accordance with standard of care.

End-of-Study (EOS)

The EOS is the last planned clinical visit for each subject enrolled in this study.

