10.6.2 Safety Endpoints

10.6.2.1 Adverse Events (AEs)

The Medical Dictionary for Regulatory Activities (MedDRA) version 19.1 or later will be used to code all AE to a system organ class and a preferred term. The subject incidence of AEs will be summarized for all treatment-emergent, serious treatment-emergent, those leading to withdrawal of IP, fatal, and events of interest (EOI), where treatment refers to IP. The identification of EOI is a continuous process. Events may be identified and documented as the safety profile of the drug is characterized. The severity of each AE will be graded using common terminology for AE (CTCAE) version 4.0 criteria.

Statistical Analysis Plan: 20140207

Date: 17 May 2017 Page 24

Subject incidence of all treatment-emergent, serious treatment-emergent, those leading to withdrawal of IP, and fatal AE will be tabulated by system organ class and preferred term, where treatment refers to IP. Where appropriate, the tables will also be presented by worst grade. The above AE tables will not be created if two or fewer subjects experience the AE. The above AE tables will be summarized separately for events occurring between Day 1 and Day 7 following administration of IP and events occurring from Day 8 onwards following administration of IP and the second dose of PACAP-38.

For PACAP-38 related treatment-emergent AEs, all treatment-emergent AEs where the question "Is there a reasonable possibility that the event may have been caused by PACAP-38?" is ticked "yes" will be summarized by treatment group.

Details of each AE will be listed.

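### Endpoint headaches and migraine-like attacks fall under two unlinked AE recording rules, and the Day 8 onwards by-arm AE tables do not separate them from other adverse events

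*Protocol*

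**What the plan says.** **Recording.** Protocol 9.1.1 says of disease-related events: "Such events do not meet the definition of an Adverse Event unless assessed to be more severe than expected by the investigator". It makes an exception, requiring AE or SAE reporting "if the investigator believes there is a causal relationship between the investigational product(s)/study treatment protocol required therapies and disease worsening". Protocol 9.2.1 applies the class to the study disease: "Migraine is considered a disease related event; however, worsening of migraine" is to be reported as an AE. SAP Section 6 repeats this under Disease-Related AE: "Migraine will be considered a disease related event; however, worsening of migraines (ie. increased frequency and/or intensity) should be reported as an AE".

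Protocol 9.2.2.1 has no severity condition: "MLA and non-migraine headaches should be recorded on the headache questionnaires and on the adverse event eCRF page". Protocol 9.1.2 adds only that "Migraines and non-migraine headaches are study endpoints", without saying whether that takes them out of the AEs. Protocol 6.3.1.2 and 10.4.2 and SAP 8.1 list MLA among the adverse events reviewed at dose-level meetings.

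**Analysis.** SAP 10.6.2.1 states: "Subject incidence of all treatment-emergent, serious treatment-emergent, those leading to withdrawal of IP, and fatal AE will be tabulated". The tables are by system organ class and preferred term, also by worst grade where appropriate, and split into Days 1 to 7 and Day 8 onwards. PACAP-38-related events are summarised by treatment group. No rule flags or separates headache or MLA after the challenge.

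**The concern.** The challenge on Day 8 is meant to provoke headache and MLA, and AMG 334 is meant to prevent them. If those events count as AEs, an effective drug shows fewer AEs after Day 8 because it works, which says nothing about its tolerability. Treatment-emergent AEs are a secondary endpoint (Protocol 10.1.1.2), so this by-arm comparison will be read as safety evidence.

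The recording side adds a second problem. Participants enter with 1 to 5 migraine days a month (Protocol 4.1.4) and Part B follow-up runs to Day 85, so spontaneous attacks are to be expected. Under 9.2.1 such an attack is an AE only if it is worse than expected. Under 9.2.2.1 it goes on the AE page if it meets the MLA criteria, and Protocol 3.1 defines MLA by symptoms and resemblance to the usual attack, with no condition on trigger or timing.

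**Working it through.** **1. The plan's own figure.** Inputs from Protocol 10.2 and 10.4.1: MLA in 70% on placebo and 20% on AMG 334; 8 per arm at the interim, then 18 per arm. The interim stops for failure if 3 or fewer placebo subjects have an MLA or if AMG 334 has more MLAs than placebo. It stops for success at a difference of at least 75%. The final test is one-sided Fisher's exact at 0.1. Exact binomial enumeration gives 6.0% interim failure, 19.5% early success and 91.0% overall success, against the stated 91%. The design calculation uses MLA occurrence only, so the AE recording rule does not enter it.

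**2. Which rule was followed in Part A.** Protocol 2.4 reports 0, 2 and 1 MLAs in Cohorts 1, 2 and 3, with 2, 3 and 2 subjects.
- MLAs: (0 + 2 + 1) / 7 = 3/7 = 42.9%.
- Reported AE incidence of migraine: 42.9%.

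The two agree, which suggests that induced MLAs were entered as AEs. Headache does not match as neatly. Its AE incidence is 71.4% = 5/7, whereas the text describes 3 subjects with headache but no MLA and 3 + 3 = 6 with either.

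**3. Size in the Part B tables if 9.2.2.1 is followed.** Expected subjects with an MLA recorded as an AE = number per arm × MLA rate.
- Placebo: 18 × 0.70 = 12.6
- AMG 334: 18 × 0.20 = 3.6
- Difference: 12.6 − 3.6 = 9.0 subjects, or 50 percentage points

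This is the primary endpoint contrast appearing again as safety data. For the first 16 subjects it is 8 × 0.70 = 5.6 v 8 × 0.20 = 1.6. The documents give no assumed headache rate on AMG 334, so the headache part cannot be sized.

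**4. Size if only attacks worse than expected are recorded.** Let w be the share of MLAs so judged. The documents give no value, so w is an assumption. Expected count = 18 × rate × w.

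| w | Placebo | AMG 334 |
|---|---|---|
| 0 | 0 | 0 |
| 0.25 | 3.15 | 0.9 |
| 0.5 | 6.3 | 1.8 |
| 1 | 12.6 | 3.6 |

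**5. Where these events land.** All challenge-induced events fall in the Day 8 onwards tables. On its preferred-term row an MLA can be recognised. In the system organ class row and the worst-grade counts it is merged with other events.

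**The case against.** The strongest reply is that the rules can be read together. Protocol 9.1.1 concerns events due to the underlying disease, whereas a Day 8 attack is provoked by a protocol-required agent. The causality exception and the more specific 9.2.2.1 then make it an AE. The dose-review wording that counts MLA among AEs and the Part A match point the same way. For challenge-induced attacks this largely stands, so a reader who inferred two irreconcilable rules would go too far. It does not settle spontaneous attacks. Neither document states the distinction, and Protocol 9.1.2 uses the plain word for migraine when naming the endpoints, so the terms are not kept apart.

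Three stronger readings are tempting and are not supported:
- **The events might vanish from the AE tables.** The 0 v 0 row above requires every MLA to be left off the AE page despite 9.2.2.1 and the causality exception.
- **Recording will vary by site.** The study plans about three sites, but nothing shows that they apply different rules. It is only a possible consequence of unclear text.
- **The worst-grade table will be driven by the endpoint.** The one grade 3 AE reported in Cohorts 1 to 3 was an MLA, but that is one event in seven subjects.

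Existing provisions also limit the harm. The Day 1 to 7 table is free of challenge-induced events, preferred terms are shown, every AE is listed, and no AE test is planned. Flushing was reported in all seven subjects in Protocol 2.4, so an any-AE row may hardly move.

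Finally, the SAP refers to Protocol Amendment 4, whereas the protocol reviewed is Amendment 3. SAP 10.6.2.1 cites a PACAP-38-specific causality question that is absent from the 9.2.2.1 reviewed here, so AE collection may have been revised. The SAP still contains both the Section 6 definition and the Section 8.1 wording, and the gap in 10.6.2.1 remains.

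**Conclusion.** The point holds as an inexpensive improvement to the reading of the safety tables. The recording rules need reconciling, chiefly for spontaneous attacks. On the rule that appears to be in use, the Day 8 onwards system organ class and worst-grade rows would partly restate efficacy, by about 12.6 v 3.6 subjects with an MLA. That size assumes the planned 70% and 20% rates, 18 per arm without conditioning on the interim outcome, and every MLA entered on the AE page. A reader might infer that the efficacy result is in doubt. It is not, because MLA occurrence is determined from the headache questionnaire and compared separately by Fisher's exact test (SAP 10.5).

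**What to change.** - **Recording rule.** Reconcile Protocol 9.1.1, 9.2.1 and 9.2.2.1 and SAP Section 6 into one rule that says how challenge-induced attacks and spontaneous attacks are each recorded.
- **Flag.** In SAP 10.6.2.1, mark headaches and MLAs with onset within 24 hours of PACAP-38 as endpoint events.
- **Added tables.** Produce a Day 8 onwards treatment-emergent summary and a worst-grade summary by arm that exclude the flagged events.
- **Keep.** Leave the full treatment-emergent table and the PACAP-38-related table complete. PACAP-38 tolerability is a stated objective (Protocol 1.3), and taking headache and MLA out would remove two of its commonest known effects.

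The cost is a clarifying sentence in each document, one dataset flag and one extra set of tables. No sample size or decision rule changes.
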